### Phase III-IV liver chemistry increased monitoring criteria with continued therapy

Liver Chemistry Increased Monitoring Criteria – Liver Monitoring Event	
Criteria	Actions

ALT <math>\geq</math>5xULN and <8xULN and bilirubin <2xULN without symptoms believed to be related to liver injury or hypersensitivity, and who can be monitored weekly for 2 weeks.
 
OR
 
ALT <math>\geq</math>3xULN and <5xULN and bilirubin <2xULN without symptoms believed to be related to liver injury or hypersensitivity, and who can be monitored weekly for 4 weeks.
	
 
• Notify the GSK medical monitor within 24 hours of learning of the abnormality to discuss subject safety.
 
• Subject can continue study treatment
 
• Subject must return weekly for repeat liver chemistries (ALT, AST, alkaline phosphatase, bilirubin) until they resolve, stabilise or return to within baseline
 
• If at any time subject meets the liver chemistry stopping criteria, proceed as described above
 
• If ALT decreases from ALT <math>\geq</math>5xULN and <8xULN to <math>\geq</math>3xULN but <5xULN, continue to monitor liver chemistries weekly.
 
• If, after 4 weeks of monitoring, ALT <3xULN and bilirubin <2xULN, monitor subjects twice monthly until liver chemistries normalize or return to within baseline.
 

## 12.4. Appendix 4: Definition of and Procedures for Recording, Evaluating, Follow-Up and Reporting of Adverse Events

### 12.4.1. Definition of Adverse Events

#### Adverse Event Definition:

- An AE is any untoward medical occurrence in a patient or clinical investigation subject, temporally associated with the use of a medicinal product, whether or not considered related to the medicinal product.
- NOTE: An AE can therefore be any unfavorable and unintended sign (including an abnormal laboratory finding), symptom, or disease (new or exacerbated) temporally associated with the use of a medicinal product.

#### Events meeting AE definition include:

- Any abnormal laboratory test results (hematology, clinical chemistry, or urinalysis) or other safety assessments (e.g., ECGs, radiological scans, vital signs measurements), including those that worsen from baseline, and felt to be clinically significant in the medical and scientific judgement of the investigator.
- Exacerbation of a chronic or intermittent pre-existing condition including either an increase in frequency and/or intensity of the condition.
- New conditions detected or diagnosed after study treatment administration even though it may have been present prior to the start of the study.
- Signs, symptoms, or the clinical sequelae of a suspected interaction.
- Signs, symptoms, or the clinical sequelae of a suspected overdose of either study treatment or a concomitant medication (overdose per se will not be reported as an AE/SAE unless this is an intentional overdose taken with possible suicidal/self-harming intent. This should be reported regardless of sequelae).
- "Lack of efficacy" or "failure of expected pharmacological action" per se will not be reported as an AE or SAE. However, the signs and symptoms and/or clinical sequelae resulting from lack of efficacy will be reported if they fulfil the definition of an AE or SAE.

#### Events NOT meeting definition of an AE include:

- Any clinically significant abnormal laboratory findings or other abnormal safety assessments which are associated with the underlying disease, unless judged by the investigator to be more severe than expected for the subject's condition.
- The disease/disorder being studied or expected progression, signs, or symptoms of the disease/disorder being studied, unless more severe than expected for the subject's

condition.

- Medical or surgical procedure (e.g., endoscopy, appendectomy): the condition that leads to the procedure is an AE.
- Situations where an untoward medical occurrence did not occur (social and/or convenience admission to a hospital).
- Anticipated day-to-day fluctuations of pre-existing disease(s) or condition(s) present or detected at the start of the study that do not worsen.

#### 12.4.2. Definition of Serious Adverse Events

If an event is not an AE per definition above, then it cannot be an SAE even if serious conditions are met (e.g., hospitalization for signs/symptoms of the disease under study, death due to progression of disease, etc).

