## 7.3. Efficacy

Efficacy of sirukumab in GCA will be assessed from the presence of GCA activity including investigator assessment of signs and symptoms of GCA (new onset localized headache, scalp or temporal artery tenderness, reduced or absent pulsation in temporal artery, cord-like thickening of temporal artery, stroke, scalp necrosis, pain over face/scalp arteries, or otherwise unexplained mouth or jaw pain upon mastication [i.e., jaw claudication]); visual signs and symptoms (including but not limited to transient or episodic blurry vision, diplopia, scotoma, ischemia-related vision loss [permanent vision loss due to AION], amaurosis fugax); PMR symptoms [shoulder and/or hip girdle pain associated with inflammatory stiffness]; other features associated with GCA such as new or worsened extremity claudication and fever of unknown origin; and laboratory results for serum ESR and CRP levels (blinded to investigator).

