#### **7.5.1.4. Cardiovascular and Death Events**

For any cardiovascular events detailed in Appendix 4 and all deaths, whether or not they are considered SAEs, specific Cardiovascular (CV) and Death sections of the CRF will be required to be completed. These sections include questions regarding CV (including sudden cardiac death) and non-CV death.

The CV CRFs are presented as queries in response to reporting of certain CV MedDRA terms. The CV information should be recorded in the specific cardiovascular section of the CRF within one week of receipt of a CV Event data query prompting its completion.

The Death CRF is provided immediately after the occurrence or outcome of death is reported. Initial and follow-up reports regarding death must be completed within one week of when the death is reported.

In the sirukumab clinical programs, significant changes in lipid laboratory parameters have been observed, as with other agents that block IL-6. The clinical significance of these changes is not known. Nonetheless, serious CV events are considered AEs of special interest and will be closely monitored in the sirukumab program. In order to fully understand CV events in this study, Major Adverse Cardiovascular Events (MACE), defined as myocardial infarction, stroke, death, hospitalization for unstable angina, and hospitalization for TIA, will be collected and prospectively adjudicated by an external CEC. The CEC is an independent committee composed of external specialists, blinded to treatment assignment, who will be commissioned to review case information on serious CV events. This will allow external review of cases and determination of diagnosis prior to analysis.

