### 12.4.3. Definition of Cardiovascular Events

Cardiovascular Events (CV) Definition:

Investigators will be required to fill out the specific CV event page of the CRF for the following AEs and SAEs:
 
 
Myocardial infarction/unstable angina
 
Congestive heart failure
 
Arrhythmias
 
Valvulopathy
 
Pulmonary hypertension
 

- Cerebrovascular events/stroke and transient ischemic attack
- Peripheral arterial thromboembolism
- Deep venous thrombosis/pulmonary embolism
- Revascularization

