9.1.7. Death

Fatal SAEs will be listed. Listings of death certificate details and cause of death will be generated to provide subject-specific details on subjects who died prior to study completion.

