9.6.3. Columbia-Suicide Severity Rating Scale

Suicidality assessments are completed at every visit (i.e. at Week 0, Week 2, Week 4, Week 8, Week 12, Week 16, Week 20, Week 24, Week 28, Week 32, Week 36, Week 40, Week 44, Week 48 and Week 52). Assessments are done using the C-SSRS. If a "yes" response is given to any suicidal behavior (not including self-injurious behavior) or a "yes" response to suicidal ideation questions 3, 4 or 5 on the C-SSRS, the investigator will be prompted to discuss the alert with the subject. A standard PSRAE (Possible suicidality-related AE) data collection form is available that is intended to collect detailed information on the circumstances of reported AEs which, in the investigator's opinion, are possibly suicidality-related. A summary table of C-SSRS post-baseline results will be provided. All C-SSRS and Possible Suicidality Related Questionnaire information will be listed in detail.

10. IDMC Reviews

An Independent Data Monitoring Committee (IDMC) will monitor data from this study. The overall responsibility of the IDMC is to protect the ethical and safety interests of subjects recruited into 201677 while protecting as far as possible the scientific validity of the data.

The IDMC will make recommendations concerning conduct of the study, including changes to the informed consent. The IDMC will meet at predefined times to identify potential treatment harm and all-cause mortality/morbidity.

After the initial organizational meeting, the first data review meeting will be held once 12 subjects have completed 12 weeks of treatment. Thereafter, the frequency of scheduled meetings depends on subject enrollment, information accumulated and safety event rates but will occur no less than quarterly.

Full details are provided in the IDMC charter document (dated 20JAN2016).

Due to study termination, the IDMC agreed to have the last formal meeting on Oct 25, 2017. Monthly cumulative SAE listing are sent to the IDMC until study end (LSLV). If the committee has any inquiries regarding safety, they can raise it with PPD and GSK even though no additional formal IDMC meeting is scheduled.

11. Part B

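### Appendix 4's exclusion of GCA events conflicts with the death, MACE and special-interest rules, so a stroke or death attributed to GCA may be missing from by-arm safety counts

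*Protocol*

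**What the plan says.** **What is excluded.** Protocol Appendix 4 (12.4.1) lists among events that are not AEs: "The disease/disorder being studied or expected progression, signs, or symptoms of the disease/disorder being studied". The sentence goes on to except anything more severe than would be expected in that subject, but no section says how this is judged. Section 12.4.2 carries the exclusion over to seriousness: "If an event is not an AE per definition above, then it cannot be an SAE even if serious conditions are met". Its examples include "death due to progression of disease".

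**What is required elsewhere.**
- Section 7.5.1.4 defines MACE to include stroke and death, has it collected and adjudicated by the blinded CEC, and requires a Death section of the CRF for every death regardless of SAE status.
- Section 7.5.1.3 makes total or partial blindness, limb claudication, and scalp or tongue necrosis AEs of special interest.

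**How the outputs are fed.**
- On the cardiovascular page, 12.4.3 says: "Investigators will be required to fill out the specific CV event page of the CRF for the following AEs and SAEs". Section 7.5.1.4 says: "The CV CRFs are presented as queries in response to reporting of certain CV MedDRA terms".
- SAP 9.1.8 identifies special-interest events, MACE among them, by adjudicating AE terms. SAP 9.1.9 starts from AEs and SAEs.
- SAP 9.1 and 9.1.4 count fatal serious TEAEs, and 9.1.1 gives exposure-adjusted rates for fatal serious AEs. Under SAP 9.1.7, "Fatal SAEs will be listed", together with listings of death certificate details and cause of death.
- SAP Section 10 gives the IDMC an all-cause mortality and morbidity remit. After its last formal meeting on 25 October 2017, it is sent a monthly SAE listing.

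**The concern.** Some of the gravest outcomes in this disease fit both sets of rules. Stroke is an assessed sign of GCA and also a MACE component. A fatal course of GCA is a non-SAE under one section and a MACE component under another. No section says which rule prevails, so whether such an event enters the AE database turns on the investigator's attribution to GCA and on an undefined judgement of severity.

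The by-arm safety counts are at stake. In a trial of this size serious cardiovascular events and deaths will be few, and one omitted event can change the table. Attribution to GCA could also be related to treatment, because the design expects better disease control on sirukumab.

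**Working it through.** The plan states no figure for strokes or deaths attributed to GCA, so there is none to reproduce. The main check follows an event through the documents. A rough sum on assumed rates then gives the scale.

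**A stroke the investigator attributes to GCA**
1. Protocol 7.3 lists it as a sign of GCA: "cord-like thickening of temporal artery, stroke, scalp necrosis". Section 4.1 and inclusion criterion 2 do the same.
2. Under 12.4.1 it is not an AE unless judged more severe than expected. The provision there on consequences of lack of efficacy does not settle the matter: they are reported only if they already meet the AE or SAE definition.
3. If it is not an AE, 12.4.2 says it cannot be an SAE. The cardiovascular page in 12.4.3 is then not called for, and the CRF query in 7.5.1.4 has no reported term to trigger it. The 24-hour rule in 7.5.1.3 refers to cardiovascular AEs and waives only the SAE threshold.
4. SAP 9.1.8 and 9.1.9 work from AE and SAE records, so the stroke is absent from the by-arm MACE counts and may not reach the CEC.
5. It may still appear in the SAP 9.4 summary of GCA signs by scheduled visit. That is not an adjudicated cardiovascular count.

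**A death attributed to GCA progression**
1. Section 12.4.2 names it as an example of a non-SAE.
2. Section 7.5.1.4 still requires the Death CRF, so the death is on record.
3. The counts and rates in SAP 9.1, 9.1.1 and 9.1.4 use fatal serious events only. The death would appear in the SAP 9.1.7 listings but in no count or rate of fatal events by arm.
4. As a non-SAE it would not be in the monthly SAE listing sent to the IDMC after termination.

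**Vision loss, claudication, scalp necrosis**

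Protocol 5.1 and 7.3 list ischaemia-related vision loss, extremity claudication and scalp necrosis as features of GCA. Section 7.5.1.3 makes closely matching events AEs of special interest. The two rules give opposite answers for the same event.

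**Scale, on stated assumptions**
- Inputs from Protocol 4.2.1 and 9.2.1: 34 subjects in Arm D with 30% sustained remission; 51 in Arm A with 70%.
- Subjects without sustained remission: Arm D 34 × 0.70 = 23.8; Arm A 51 × 0.30 = 15.3.
- Assumption, not from the documents: a fraction q of these has a GCA-attributed stroke or death, and none is reported as an AE.
- q = 1% to 3%: Arm D 23.8 × q = 0.24 to 0.71; Arm A 15.3 × q = 0.15 to 0.46 events.
- q = 5%: 1.19 and 0.77. q = 10%: 2.38 and 1.53.

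Non-remission is only a stand-in for active disease. Under Protocol 9.4.1 it also covers withdrawal, treatment discontinuation and departure from the taper. Conversely, every subject had active disease within 6 weeks of baseline. Applying 3% to all subjects gives 34 × 0.03 = 1.0 and 51 × 0.03 = 1.5. These are orders of magnitude only.

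**The case against.** The strongest reply is that the specific rules already override the template wording.

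- **The severity exception.** Section 12.4.2 is conditional on the AE definition, so the exception in 12.4.1 carries through to SAEs. Entry requires clinically stable disease, and a new stroke or a death in such a subject could readily be judged more severe than expected. This stands against any reading that a GCA stroke or death can never be reported. It does not secure reporting, because the exception is undefined and 12.4.2 itself offers fatal progression as a non-SAE.
- **Separate capture.** A reader might infer that deaths vanish from the record. They do not: the Death CRF covers all of them, SAP 9.1.7 lists cause of death, and 7.5.1.4 sends MACE to the CEC without excluding GCA causes. What remains is that the counts and rates of fatal events use SAE data, and the cardiovascular form depends on a reported term.
- **The IDMC.** A reader might infer that the committee could miss deaths throughout the trial. The documents do not support that. The SAE listing is described only for the period after the last formal meeting, and earlier report content is in a charter not supplied.
- **Uneven loss by arm.** It is tempting to say that events do drop out unevenly and to compute a distorted relative risk. The documents give no rate of GCA-attributed events and no reporting fraction, non-remission is not the same as active disease, and investigators are blinded in Part A. Blinding does not equalise how often GCA is active, and ESR alerts above 40 mm/hr (Protocol 6.4) give a cue that IL-6 blockade may itself affect. So greater loss on placebo is possible but not shown. If it occurred, it would tend to understate a benefit of sirukumab rather than hide a harm.
- **Timing.** The study has ended, so new AE wording cannot by itself recover treatment-period events. That is correct, and it makes the death table the most useful of the changes.

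**Conclusion.** The point holds as a conflict between sections. Followed as written, 12.4.1 and 12.4.2 allow a stroke or death attributed to GCA to be left out of the AE/SAE-based by-arm counts, while 7.5.1.3 and 7.5.1.4 intend such events to be captured. Loss is possible, not certain, and may be more frequent on placebo.

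The size is unknown. At planned enrolment, with 1% to 3% of non-remitters affected and none reported, fewer than one event per arm is lost; about one per arm is a reasonable upper figure unless the rate is well above that. The study stopped early and the SAP does not give the number randomised. The conclusion rests on the text of the sections; the scale rests on assumed rates. It is worth correcting because the events are the most serious ones and the remedy is cheap.

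**What to change.** 1. **Protocol 12.4.1 and 12.4.2, reconciled with 7.5.1.3 and 7.5.1.4.** State that all deaths, all MACE components and the listed special-interest events (blindness, limb claudication, scalp or tongue necrosis) are recorded as AE or SAE whatever their attribution to GCA. Add a GCA-attributed flag and send MACE components to the CEC.
2. **SAP 9.1.7.** Tabulate all-cause deaths by actual arm from the Death CRF, beside the fatal-SAE table.
3. **SAP Section 10.** Include all deaths, not only fatal SAEs, in the remaining IDMC listings.

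The cost is reconciling wording, one table from data already collected, and a small addition to a listing. The drawback is that some GCA events will enter the AE tables; the flag lets them be shown separately. Items 2 and 3 do not depend on the AE wording being changed.

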**Serious Adverse Event (SAE) is defined as any untoward medical occurrence that, at any dose:**

**a. Results in death**

**b. Is life-threatening**

NOTE:

The term 'life-threatening' in the definition of 'serious' refers to an event in which the subject was at risk of death at the time of the event. It does not refer to an event, which hypothetically might have caused death, if it were more severe.

**c. Requires hospitalization or prolongation of existing hospitalization**

NOTE:

- In general, hospitalization signifies that the subject has been detained (usually involving at least an overnight stay) at the hospital or emergency ward for observation and/or treatment that would not have been appropriate in the physician's office or out-patient setting. Complications that occur during hospitalization are AEs. If a complication prolongs hospitalization or fulfills any other serious criteria, the event is serious. When in doubt as to whether "hospitalization" occurred or was necessary, the AE should be considered serious.
- Hospitalization for elective treatment of a pre-existing condition that did not worsen from baseline is not considered an AE.

**d. Results in disability/incapacity**

NOTE:

- The term disability means a substantial disruption of a person's ability to conduct normal life functions.

 
This definition is not intended to include experiences of relatively minor medical significance such as uncomplicated headache, nausea, vomiting, diarrhea, influenza, and accidental trauma (e.g. sprained ankle) which may interfere or prevent everyday life functions but do not constitute a substantial disruption.
 

e. Is a congenital anomaly/birth defect

f. Other situations:
 
 
Medical or scientific judgment should be exercised in deciding whether reporting is appropriate in other situations, such as important medical events that may not be immediately life-threatening or result in death or hospitalization but may jeopardize the subject or may require medical or surgical intervention to prevent one of the other outcomes listed in the above definition. These should also be considered serious.
 
Examples of such events are invasive or malignant cancers, intensive treatment in an emergency room or at home for allergic bronchospasm, blood dyscrasias or convulsions that do not result in hospitalization, or development of drug dependency or drug abuse.
 

g. Is associated with liver injury and impaired liver function defined as:
 
 
ALT <math>\geq</math> 3xULN and total bilirubin* <math>\geq</math> 2xULN (>35% direct), or
 
ALT <math>\geq</math> 3xULN and INR** <math>></math> 1.5.
 
 
* Serum bilirubin fractionation should be performed if testing is available; if unavailable, measure urinary bilirubin via dipstick. If fractionation is unavailable and ALT <math>\geq</math> 3xULN and total bilirubin <math>\geq</math> 2xULN, then the event is still to be reported as an SAE.
 
** INR testing not required per protocol and the threshold value does not apply to subjects receiving anticoagulants. If INR measurement is obtained, the value is to be recorded on the SAE form.

### 12.4.3. Definition of Cardiovascular Events

Cardiovascular Events (CV) Definition:

Investigators will be required to fill out the specific CV event page of the CRF for the following AEs and SAEs:
 
 
Myocardial infarction/unstable angina
 
Congestive heart failure
 
Arrhythmias
 
Valvulopathy
 
Pulmonary hypertension
 

- Cerebrovascular events/stroke and transient ischemic attack
- Peripheral arterial thromboembolism
- Deep venous thrombosis/pulmonary embolism
- Revascularization

#### 12.4.4. Recording of AEs and SAEs

##### AEs and SAE Recording:

- When an AE/SAE occurs, it is the responsibility of the investigator to review all documentation (e.g., hospital progress notes, laboratory, and diagnostics reports) relative to the event.
- The investigator will then record all relevant information regarding an AE/SAE in the CRF.
- It is **not** acceptable for the investigator to send photocopies of the subject's medical records to GSK in lieu of completion of the GSK, AE/SAE CRF page.
- There may be instances when copies of medical records for certain cases are requested by GSK. In this instance, all subject identifiers, with the exception of the subject number, will be blinded on the copies of the medical records prior to submission of to GSK.
- The investigator will attempt to establish a diagnosis of the event based on signs, symptoms, and/or other clinical information. In such cases, the diagnosis will be documented as the AE/SAE and not the individual signs/symptoms.
- Subject-completed Value Evidence and Outcomes questionnaires and the collection of AE data are independent components of the study.
- Responses to each question in the Value Evidence and Outcomes questionnaire will be treated in accordance with standard scoring and statistical procedures detailed by the scale's developer.
- The use of a single question from a multidimensional health survey to designate a cause-effect relationship to an AE is inappropriate.

